10.12 Carfilzomib Safety Considerations

Based upon the experience in the Phase 1 and 2 clinical studies with Carfilzomib, the following observations are noted:

- A “first dose effect” has been seen, which is notable for fever, chills, rigors, and/or dyspnoea occurring during the evening following the first day of infusion and an increase in creatinine on Day 2, which may be the clinical sequelae of rapid tumour lysis and/or cytokine release.
- Should a “first dose” effect occur at any point during Cycle 1 or 2, treatment with high dose glucocorticoids (e.g. methylprednisolone 50–100 mg) is recommended. In addition, intravenous fluids, vasopressors, oxygen, bronchodilators, and acetaminophen should be available for immediate use and instituted, as medically indicated.
- Dexamethasone will be administered prior to all Carfilzomib doses to prevent infusion reactions. See section 9.3.3 for more details.
- Acyclovir or similar should be given to all participants with a history of herpes simplex or zoster, per institutional prophylaxis guidelines, unless contraindicated.
- CrCl changes are mostly transient, reversible, and non-cumulative. All participants should be well hydrated. Clinically significant electrolyte abnormalities should be corrected prior to dosing with Carfilzomib. Renal function must be monitored closely during treatment with Carfilzomib. Serum chemistry values, including creatinine, must be obtained and reviewed prior to each dose of Carfilzomib during Cycles 1 and 2. Carfilzomib must be withheld for participants with a CrCl $<$ 15 mL/min at any time during study participation.
- Participants with active or suspected infection of any kind that required systemic treatment should not be dosed with Carfilzomib until the infection has resolved.
- Cases of gastrointestinal, pulmonary, and intracranial haemorrhage have been reported in patients treated with Carfilzomib, and are often associated with thrombocytopenia. Thrombocytopenia has been transient, with platelet nadirs seen between Day 8 and Day 15 of dosing, and typically resolves to baseline by the start of the next cycle. Platelet counts should be monitored frequently during treatment with Carfilzomib. For platelet counts $\leq 10 \times 10^9/L$ with evidence of bleeding, Carfilzomib dosing must be withheld. If platelet counts do not recover, the dose of Carfilzomib may be reduced or held according to the Dose Reductions / Adjustments rules outlined in Section 10.4.
- Thromboembolic events, including deep vein thrombosis and pulmonary embolisms, have been reported in patients taking Carfilzomib, and some events have had fatal outcomes. Thromboprophylaxis, as outlined in section 9.2, should be administered to all participants receiving Carfilzomib.
- Participants should have anaemia corrected in accordance with the Institutional guidelines.
- Carfilzomib treatment can cause nausea, vomiting, diarrhoea, or constipation sometimes requiring the use of antiemetics or antidiarrhoeals. Fluid and electrolyte replacement should be administered to prevent dehydration.
- Posterior reversible encephalopathy syndrome (PRES), formerly termed reversible posterior leukoencephalopathy syndrome (RPLS), is a rare neurological disorder, which can present with seizure, headache, lethargy, confusion, blindness, altered consciousness, and other visual and neurological disturbances, along with hypertension. The diagnosis is confirmed by neuro-radiological imaging. If diagnosed early and treated, the symptoms of PRES may be reversed. Cases of PRES have been reported in subjects receiving Carfilzomib. Discontinue Carfilzomib if PRES is suspected. Refer to the study protocol for further instructions regarding dose modifications. The safety of reinitiating Carfilzomib therapy in subjects previously experiencing PRES is not known.
- Cases of thrombocytopenic thrombotic purpura/hemolytic uremic syndrome (TTP/HUS) including those with fatal outcome have been reported in subjects who received Carfilzomib. Monitor for signs and symptoms of TTP/HUS. If the diagnosis is suspected, stop Carfilzomib and manage per standard of care including plasma exchange as clinically appropriate. If the diagnosis of TTP/HUS is excluded, Carfilzomib can be restarted.
- Hypertensive crises have been infrequently reported in subjects treated with Carfilzomib. Hypertensive crises can present as hypertensive urgency or as a hypertensive emergency. Hypertensive urgency is defined as sustained or persistent systolic blood pressure 180mmHg or higher or diastolic blood pressure 110mmHg or higher, with no associated organ damage. A hypertensive emergency occurs when blood

pressure reaches levels that result in end organ damage. All patients should be routinely evaluated for hypertension and treated as needed. If the hypertension cannot be controlled Carfilzomib should be reduced, per protocol. In cases of hypertensive crises, stop Carfilzomib until resolved or returned to baseline and consider whether to restart Carfilzomib based on a risk/benefit assessment.

- Cases of pulmonary hypertension have been commonly reported in subjects treated with Carfilzomib. Pulmonary hypertension is generally defined as a mean pulmonary arterial pressure ≥ 25 mmHg at rest. Echocardiography is usually the first test to suggest pulmonary hypertension. Pulmonary hypertension can be a progressive, fatal disease if untreated, although the rate of progression is highly variable. Amyloid patients often have pulmonary hypertension at baseline. Stop Carfilzomib until pulmonary hypertension has resolved or returned to baseline and consider whether to restart Carfilzomib based on a risk/benefit assessment. Cases of interstitial lung disease (including pneumonitis), acute respiratory failure and Acute Respiratory Distress Syndrome (ARDS) have been uncommonly reported in subjects. Evaluate and stop Carfilzomib until resolved and consider whether to restart Carfilzomib based on a risk/benefit assessment.
- Acute respiratory distress syndrome, acute respiratory failure, and acute diffuse infiltrative pulmonary disease such as pneumonitis and interstitial lung disease have been reported in subjects receiving Carfilzomib. Suspected acute respiratory conditions should be evaluated and Carfilzomib stopped until resolution. Consider whether to re-start Carfilzomib based on a risk/benefit assessment.
- Dyspnoea is commonly reported in participants receiving Carfilzomib, and should be evaluated to exclude cardiopulmonary conditions (cardiac failure, pulmonary syndromes). Carfilzomib shall be stopped for Grade 3 or 4 dyspnoea until resolves or returned to baseline. Consider whether to re-start Carfilzomib based on a risk/benefit assessment.
- Cases of Tumor Lysis Syndrome (TLS) including fatal outcome, have been reported in subjects who received Carfilzomib. Subjects with a high tumor burden should be considered to be at greater risk for TLS. Ensure that subjects are well hydrated before administration of Carfilzomib in Cycle 1 and in subsequent cycles as needed. Uric acid-lowering drugs should be considered in subjects at high risk for TLS. Monitor for evidence of TLS during treatment, including regular measurement of serum electrolytes, and manage promptly. Interrupt Carfilzomib until TLS is resolved. Refer to the study protocol for further instructions regarding dose modifications.

Please refer to the trial supplied Investigator Brochure to see the full adverse drug reaction tables.

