^b Including haematology, biochemistry, paraprotein and immunoglobulins (see Appendix 6 for details)

^c Only if clinically indicated

^d Send to UK NAC as per standard practice. Results will be used to assess haematological response and relapse.

^e visit must be within 28 days of registration

^f Patient must receive 1st cycle of treatment within 6 weeks of reconfirmation of eligibility at the RHC (see 11.1.2).

^g Repeat echocardiogram at end of cycle 2 only (echocardiograms at baseline, prior to cycle 4 and end of treatment will be done at NAC). Echocardiogram to be repeated at any cycle if clinically indicated for unexpected worsening of cardiac function.

^h To be supervised and performed on the day of prescription or in the 3 days prior to the visit to the prescriber.

ⁱ To be supervised and performed four weeks after the end of treatment during the follow-up visit

^j FBC and creatine levels to be checked at day 8 and day 15 (see appendix 6 for details)

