11.2 Assessments during treatment

Prior to each chemotherapy cycle

During treatment the patient should be seen prior (within 3 days) to each chemotherapy cycle and the following assessments performed:

- Physical examination, including lying and 5 minute standing blood pressure.
- FBC (Hb, White Cell Count, Platelets), clotting screen (PT, APTT, Factor X (if indicated)), biochemistry (urea, creatinine, eGFR, calcium, phosphate, CRP, ALP, GGT, AST, ALT, bilirubin, albumin, sodium, potassium).
- Assess and record any adverse events
- Record concomitant medications
- Repeat echocardiogram at end of cycle 2 only (echocardiograms at baseline, prior to cycle 4 and end of treatment will be done at UK NAC). Echocardiogram to be repeated at any cycle if clinically indicated for unexpected worsening of cardiac function.
- Pregnancy test
- **A 5ml serum sample must be sent to the UK NAC as per standard practice prior to the start of each chemotherapy cycle ***

*The 5 ml serum sample is used by the UK NAC to assess haematological response and relapse (through biochemical tests including serum free light chain assessments), the results of which will be used as part of the trial dataset. The sample will be frozen and stored at the UK NAC indefinitely as per standard practice (separate written

consent is obtained for this as per standard clinical practice for all patients attending UK NAC). In addition, the following data will be collected for each treatment cycle:

- Treatment cycle number and cycle details, including dose given, dose alterations, and reasons
- Toxicities relating to treatment

Day 8 and day 15 of cycle

Patients will also be seen on day 8 and day 15 of each cycle and the following assessment performed:

- FBC (Hb, White Cell Count, Platelets) and creatinine
- Assess and record any adverse events
- Record concomitant medications

All patients with stage III disease will be assessed once weekly for the first three cycles for signs or symptoms of worsening heart failure or “red flag” symptoms .**

All patients will be given a card for “red flag” symptoms with advice to seek urgent medical attention**

** **Red Flag symptoms:** Significant worsening dyspnoea, hypotension, unexplained persistent dizziness, syncopal episodes.

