APPENDIX 6: DETAILS OF INVESTIGATIONS AND THEIR TIMINGS**PLEASE ALSO SEE PROTOCOL SECTION 11**

PLEASE NOTE – prior to starting each treatment cycle at RHC a 5ml serum sample must be collected and sent to UK NAC (see protocol section 1 for contacts).

Clinical Assessments to be performed at the following timepoints:

- Baseline at UK NAC
 - Re-confirmation of Eligibility at RHC
 - Prior to each cycle at RHC
 - UK NAC visit following 3rd cycle of study treatment
 - UK NAC visit 7.5 months after start of treatment or 1 month after the end of study treatment if 6 cycles given.
- | | |
|---|---|
| 
 • Medical History at baseline • Weight • 5 minute standing blood pressure | 
 • Physical examination • Lying blood pressure • ECOG Performance Status • NYHA heart failure class |
|---|---|

Haematology to be performed at the following timepoints:

- Baseline at UK NAC
 - Re-confirmation of Eligibility at RHC
 - Prior to each cycle at RHC and at day 8 and 15
 - UK NAC visit following 3rd cycle of study treatment
 - UK NAC visit 7.5 months after start of treatment or 1 month after the end of study treatment if 6 cycles given.
- | | |
|--|---|
| 
 • Haemoglobin • Platelets • APTT | 
 • White blood count (including differential) • PT • Factor X (if indicated) |
|--|---|

Biochemistry to be performed at the following timepoints:

- Baseline at UK NAC
 - Re-confirmation of Eligibility at RHC
 - Prior to each cycle at RHC
 - UK NAC visit following 3rd cycle of study treatment
 - UK NAC visit 7.5 months after start of treatment or 1 month after the end of study treatment if 6 cycles given.
- | | |
|---|---|
| 
 • Urea • eGFR (to be calculated as per local biochemistry laboratory standard protocol) • Phosphate • ALP • AST • Bilirubin • Potassium | 
 • Creatinine (to be checked at day 8 & day 15 of each cycle) • Calcium • CRP • GGT • ALT • Albumin • Sodium |
|---|---|

APPENDIX 6 CONTINUED OVERLEAF.....

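### Section 10.12 requires serum chemistry before every carfilzomib dose in cycles 1 and 2, but the visit schedule lists creatinine as the only chemistry-panel item on days 8 and 15, so 4 of those 6 doses have no scheduled electrolytes

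*Protocol*

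**What the plan says.** The requirement is in Protocol section 10.12, in the bullet that opens with creatinine clearance: "Serum chemistry values, including creatinine, must be obtained and reviewed prior to each dose of Carfilzomib during Cycles 1 and 2". Earlier in that bullet is the instruction "Clinically significant electrolyte abnormalities should be corrected prior to dosing with Carfilzomib". The tumour lysis bullet at the end of 10.12 adds "Monitor for evidence of TLS during treatment, including regular measurement of serum electrolytes, and manage promptly".

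The visit schedule appears in three places.

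- **Section 11.2, before each cycle.** "During treatment the patient should be seen prior (within 3 days) to each chemotherapy cycle". The laboratory work at that visit includes "biochemistry (urea, creatinine, eGFR, calcium, phosphate, CRP, ALP, GGT, AST, ALT, bilirubin, albumin, sodium, potassium", which covers all four electrolytes.
- **Section 11.2, days 8 and 15.** The laboratory line reads "FBC (Hb, White Cell Count, Platelets) and creatinine".
- **Assessment table, footnote j.** "FBC and creatine levels to be checked at day 8 and day 15" (creatine is evidently creatinine).
- **Appendix 6, Biochemistry.** The timepoints at the treating centre are pre-cycle. One analyte carries an extra instruction: "Creatinine (to be checked at day 8 & day 15 of each cycle". The haematology list in the same appendix, by contrast, names days 8 and 15 among its timepoints.

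The SAP has no laboratory schedule, so the point lies wholly within the protocol.

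**The concern.** Section 10.12 is mandatory, is worded in the plural, and names creatinine as one member of a set. The schedule that a research nurse would work from supplies that one member on days 8 and 15 and nothing else from the panel. An instruction to correct electrolytes before a dose cannot be carried out unless a result is available.

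What is at stake is patient safety at the dosing decision. Adverse events are reviewed on days 8 and 15, but an electrolyte disturbance without symptoms shows only in a blood result. Section 9.3.3 lists hypokalaemia among the reactions seen in more than 15% of patients. On day 8 of cycle 1 each patient moves from the 20 mg/m² loading dose to the registered dose (27 to 56 mg/m²), and section 10.1 holds treatment if a grade 3 or 4 toxicity follows the loading dose. A pre-dose electrolyte result would inform that decision.

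**Working it through.** The protocol gives no figure of its own here, so the check is a count and a side-by-side reading.

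**Inputs**

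- Dosing days: 1, 8 and 15 of each 28-day cycle (section 8.1.1).
- Cycles covered by the requirement: 1 and 2 (section 10.12).
- Electrolytes in the pre-cycle panel: sodium, potassium, calcium, phosphate (section 11.2, Appendix 6).
- Stated patient numbers: at most 18 in escalation and 20 in expansion (section 19.1).

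**Doses covered**

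- Doses in cycles 1 and 2 = 2 cycles × 3 days = 6.
- Doses on days 8 and 15 = 2 cycles × 2 days = 4.
- Doses with the full panel scheduled = 6 − 4 = 2 (day 1 of each cycle).

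| Dose day, cycles 1 and 2 | Creatinine scheduled | Na, K, Ca, phosphate scheduled |
|---|---|---|
| Day 1 | Yes | Yes |
| Day 8 | Yes | No |
| Day 15 | Yes | No |

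**Age of the last scheduled electrolyte result, with no delay**

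The pre-cycle panel is taken between 0 and 3 days before day 1.

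- At the day 8 dose: 8 − 1 = 7 days, up to 7 + 3 = 10 days.
- At the day 15 dose: 15 − 1 = 14 days, up to 14 + 3 = 17 days.

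**Could another scheduled test fill the gap?** NT-proBNP is taken on days 8 and 15 of cycle 1 (Appendix 6, other investigations). It is outside the biochemistry panel and is not an electrolyte. No other scheduled item applies.

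**Is the omission shorthand?** Appendix 6 adds days 8 and 15 to the haematology timepoints. Under biochemistry it attaches them to creatinine alone. The two lists are drawn differently, and section 11.2 and footnote j agree with that difference.

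**Cost of covering the four doses**

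- Stated numbers: 4 × 18 = 72 and 4 × 20 = 80, so 72 + 80 = 152 panels.
- Table 2 allows more than 18 escalation patients. If levels 0 and 1 each pass with 0 of 3, level 2 fills to six and fails, and levels 1 and 0 then fill to six and fail in turn, level −1 needs six as well. That gives 4 × 6 = 24 in escalation, 24 + 20 = 44 in all, and 4 × 44 = 176 panels.
- Replacements for non-evaluable patients would come on top of either total.

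**The case against.** The best defence is that this is an omission and not a contradiction. The schedule nowhere limits the day 8 and 15 tests to those it lists, section 9.3.3 sends readers to 10.12, and a site that follows 10.12 breaks no other rule. That stands: a site reading both sections can comply.

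The second defence concerns scope. The bullet is mainly about renal function, it names only creatinine, and creatinine is scheduled before all six doses. The four electrolytes are therefore an inference, drawn from the electrolyte sentence in the same bullet and from the tumour lysis bullet. This also stands as a limit on the claim. It does not remove the mismatch, because reading the requirement as creatinine alone gives no meaning to its plural wording and leaves the electrolyte instruction with no scheduled result.

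The third is that the clinical background is mixed. The hypokalaemia entry in 9.3.3 carries no grade. Section 2.1.3.1 reports no consistent change in potassium, calcium, phosphorus or uric acid among the phase 1 first-dose-effect patients, and 2.1.3.2 reports no further tumour lysis in more than 350 patients once prophylaxis guidelines were in place. Section 2.1.3.3 does give 25% grade 3/4 hypophosphataemia, but with lenalidomide in the regimen. This is a fair reason to keep the point small.

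A reader might go further and infer that the missing samples bias the DLT count or the MTD. The documents do not support that. They give no rate for undetected events, tests can be ordered on clinical grounds, and under section 8.1.4 an electrolyte imbalance counts as a DLT only at grade 3 or above despite adequate supportive care. Nor can the requirement be stretched to liver tests or to uric acid and LDH: section 10.12 does not name them in its pre-dose requirement, and adding them would not follow from this mismatch.

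**Conclusion.** The mismatch is real. Section 10.12 requires chemistry before all six carfilzomib doses in cycles 1 and 2, and the schedule provides electrolytes before two of them. Four doses rely on a site noticing 10.12; a site that works only from section 11.2, footnote j or Appendix 6 would not meet it.

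The count rests on the dosing days and the three schedule texts and needs no assumption. The choice of sodium, potassium, calcium and phosphate is inferred, as 10.12 lists no analytes. The 7 to 10 and 14 to 17 day intervals assume that no dose is delayed.

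This is a minor safety-alignment point. No effect on the DLT count, the MTD or any other endpoint is claimed.

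**What to change.** In section 11.2, footnote j and Appendix 6, add sodium, potassium, calcium and phosphate to the day 8 and day 15 blood tests in cycles 1 and 2, to be reviewed before carfilzomib is given. Footnote j could read: *FBC and creatinine on days 8 and 15 of every cycle; in cycles 1 and 2 also sodium, potassium, calcium and phosphate, reviewed before the carfilzomib dose.* This also corrects the misprint of creatinine.

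If the sponsor meant creatinine alone, 10.12 should say so, but the electrolyte-correction instruction would then still lack a scheduled result on those days. Adding the electrolytes is the cleaner course.

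The cost is a schedule amendment and a small laboratory charge: four panels per patient, 152 in all on the stated numbers and up to 176 if de-escalation fills four dose levels, before replacements. No visit or blood draw is added, because blood is already taken on those days.

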In PX-171-004, a first cohort of patients received 20 mg/m². The subset of patients (N=54) that had not seen bortezomib had an ORR of 46% (2% CR, 9% VGPR and 35% PR), while the bortezomib treated patients (N=33) had an ORR of 18% (3% CR, 3% VGPR and 12% PR)(32, 33). The median TTP was 7.6 and 5.3 months in these two groups, respectively. Thus, Carfilzomib can induce very high levels of response in patients who have not previously been treated with bortezomib and, even in bortezomib-treated patients, substantial anti-tumor activity is observed. Of note, disease control (PR + MR + SD) was achieved in ~65% of patients with progressive MM entering the study. Patients on these studies have been treated for >12 cycles with good tolerability and no cumulative toxicity (e.g., bone marrow, severe fatigue, or neuropathy) have not been observed. The protocol was amended to allow patients to increase to 27 mg/m² in Cycle 2 or later based on tolerability, similar to that used in PX-171-003 – A1.

In a phase 2 study, Carfilzomib was administered 20 mg/m² on days 1 to 2 of cycle 1, 56 mg/m² thereafter (30-minute infusion), in relapsed refractory myeloma (R/RMM) with the option of adding Dexamethasone (20 mg) for suboptimal response/progression (34). Forty-four patients were enrolled, all having prior bortezomib and immunomodulatory drugs and a median of 5 prior regimens. Of 42 response-evaluable patients, 23 (55%) achieved at least partial response (PR). Median (95% confidence interval) duration of response, progression-free, and overall survival were 11.7 (6.7-14.7), 4.1 (2.5-11.8), and 20.3 months (6.4-not estimable), respectively. High-risk cytogenetics did not impact outcomes. Treatment was active in bortezomib-refractory subgroups, but these patients tended to have poorer outcomes. Four/10 patients with prior allogeneic transplant achieved at least PR. Of 6 patients who responded, progressed and had Dexamethasone added, 4 achieved at least stable disease. The most frequent grade 3/4 adverse events (AEs) possibly related to Carfilzomib included lymphopenia (43%), thrombocytopenia (32%), hypertension (25%), pneumonia (18%), and heart failure (11%). Seven patients (16%) discontinued treatment due to AEs. Carfilzomib 56 mg/m² +/- Dexamethasone was tolerable and provided durable responses.

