10.5 Dose Reductions for Non-Haematologic Toxicities

Carfilzomib should be withheld for events \geq Grade 3 until resolved to \leq Grade 1 or return to baseline.

After resolution of the event to \leq Grade 1 or return to baseline, if the adverse event was not treatment-related, subsequent treatment with Carfilzomib may resume at full dose. If the event was treatment-related, subsequent treatment with Carfilzomib will resume at one level dose reduction except for nausea, vomiting or diarrhoea which can be attributed to Carfilzomib (see table 5 below). If toxicity continues or recurs, a 2nd Carfilzomib dose reduction may be permitted at the discretion of the investigator. No more than three dose reductions will be permitted in an individual participant on study. If toxicity continues or recurs after three dose reductions, the participant should be discontinued from treatment.

Dose reduction guide for Carfilzomib:

Table 4: Dose Reduction Guide for Carfilzomib Dosing

Current dose	Reduce to
27mg/m ²	20mg/m ²
36 mg/m ²	27 mg/m ²
45 mg/m ²	36 mg/m ²
56 mg/m ²	45 mg/m ²

If the participant tolerates the reduced dose for two cycles, participant may be dose escalated to the dose prior to reduction following discussion with the CI and CTRU.

Dose adjustment guidelines for non-haematologic toxicities are summarised as follows:

Table 5: Dose Adjustment Guidelines for Non-Haematological Toxicities.

Symptom	Recommended Action Carfilzomib
Allergic reaction/hypersensitivity Grade 2 – 3 Grade 4	Withhold until \leq Grade 1, reinstitute at full dose. Discontinue (refer to section 14)
Tumour lysis syndrome (≥ 3 of following: $\geq 50\%$ increase in creatinine, uric acid, or phosphate; $\geq 30\%$ increase in potassium; $\geq 20\%$ decrease in calcium; or ≥ 2 -fold increase in LDH)	Withhold Carfilzomib until all abnormalities in serum chemistries have resolved. Reinstitute at full doses.

Infection Grade 3 or 4	Withhold Carfilzomib until systemic treatment for infection complete and infection resolves. If no neutropenia, restart at same dose. If neutropenic, follow neutropenia instructions.
Herpes zoster of any grade	Withhold Carfilzomib until lesions are dry. Reinstigate at full dose
Grade 3 Nausea or vomiting despite maximal anti-emetic therapy or diarrhoea	Withhold Carfilzomib until this resolves and re-start at full dose. If recurrent, re-start at one dose level lower

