Grade 2 treatment emergent neuropathy with pain or Grade 3 neuropathy	Continue to dose. If neuropathy persists for more than two weeks hold Carfilzomib until resolved to \leq Gr 2 without pain. Then restart at 1 dose decrement
\geq Grade 3 elevation in LFTs (AST, ALT, or total bilirubin)	Withhold dose. Resume at 1 dose decrement when toxicity has resolved to baseline.
Grade 4 neuropathy	Discontinue (refer to section 14)
Renal Dysfunction Serum creatinine equal to or greater than 2 x baseline, or CrCl $<$ 15mL/min (or CrCl decreases to \leq 50% of baseline) or need for dialysis.	Withhold dose and continue monitoring renal function (serum creatinine or serum creatinine clearance). If attributable to Carfilzomib, resume when renal function has recovered to within 25% of baseline. Start at 1 dose level reduction. If not attributable to Carfilzomib, dosing may be resumed at the discretion of the physician. If tolerated, the reduced dose may be escalated to the previous dose at the discretion of the physician. For patients on dialysis during Carfilzomib, the dose is to be administered after the dialysis procedure.
Congestive heart failure and other cardiopulmonary disorders.	See section 10.10. Any participant with marked worsening of symptoms of congestive heart failure, whether or not drug related, must have the dose withheld until resolution or return to baseline, after which treatment may continue at a reduced dose, or the subject may be permanently discontinued
Other non-haematologic toxicity assessed as Carfilzomib-related \geq Grade 3	Withhold dose until toxicity resolves to \leq Grade 2 or baseline. Restart at 1 dose decrement. If tolerated, the reduced dose may be escalated to the previous dose at the discretion of the physician.
PRES (posterior reversible encephalopathy syndrome with symptoms including headaches, altered mental status, seizures, visual loss, and hypertension).	If PRES suspected, withhold Carfilzomib. Consider evaluation with neuroradiological imaging for onset of visual or neurological symptoms suggestive of PRES. If PRES diagnosis is excluded, Carfilzomib administration may resume if clinically appropriate.

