10.11 Conditions Not Requiring Dose Reduction

The following conditions are exceptions to the above guidelines. Carfilzomib dosing does not need to be withheld in the following cases:

- Grade 3 nausea, vomiting or diarrhoea (unless persisting >5 days with adequate use of anti-emetics or anti-diarrhoeal medication)
- Grade 3 fatigue (unless persisting for >14 days)

- Alopecia
- \geq Grade 3 hyperglycaemia attributed to Dexamethasone

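### Carfilzomib instructions for pulmonary hypertension conflict between protocol 10.12 (stop at any grade) and 10.5 (hold from grade 3), with no stated precedence; a smaller gap of the same kind exists for systemic hypertension

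*Protocol*

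**What the plan says.** **General rule.** Protocol 10.5 states "Carfilzomib should be withheld for events" of grade 3 or above, until grade 1 or baseline. If the event was treatment-related, "subsequent treatment with Carfilzomib will resume at one level dose reduction except for nausea, vomiting or diarrhoea". Table 5 has no row for pulmonary or systemic hypertension. Its catch-all row, "Other non-haematologic toxicity assessed as Carfilzomib-related" at grade 3 or above, also holds and restarts one decrement lower. Section 10.2 delays treatment for grade 3/4 non-haematological toxicity in subsequent cycles. Section 10.11, introduced by "Carfilzomib dosing does not need to be withheld in the following cases", lists gastrointestinal events, fatigue, alopecia and hyperglycaemia, but neither form of hypertension.

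**Event-specific text in 10.12.** For pulmonary hypertension: "Stop Carfilzomib until pulmonary hypertension has resolved or returned to baseline", then a risk/benefit decision on restarting. No grade is given. For systemic hypertension: evaluate, treat as needed, and "If the hypertension cannot be controlled Carfilzomib should be reduced, per protocol". In a hypertensive crisis carfilzomib is stopped until resolution or baseline, and restart is again a risk/benefit decision.

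**Which section to use.** Section 9.3.3 names the topics managed under 10.12 (tumour lysis, creatinine clearance, infection, anaemia, thrombocytopenia, gastrointestinal toxicity), sends cardiac toxicities to 10.10 and sends other toxicities to 10.4 and 10.5. The end of 10.2 sends toxicities to Tables 3 and 5, apart from neuropathic pain and peripheral sensory neuropathy. Neither statement says whether 10.12 overrides the tables where it gives its own instruction.

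**The concern.** A site that follows the routing in 9.3.3 and 10.2 applies the grade 3 threshold to pulmonary hypertension. A site that reads 10.12 stops carfilzomib at any grade. The situation is foreseeable: 10.12 describes pulmonary hypertension as commonly reported with carfilzomib and often present at baseline in amyloid patients, and exclusion criterion 11 in 6.3.2 removes only severe cases judged likely to interfere with adherence.

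Patient safety is at stake first. On the statistical side, whether a dose is held feeds the number of patients with dose delays and the relative dose intensity (protocol 18.3 and 19.4; SAP 2.3.2). In escalation cycle 1 it can also feed DLT criterion 4 in 8.1.4. If sites differ in which section they follow, these summaries partly reflect the section used rather than the regimen.

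**Working it through.** The plan states no figure on this point, so the check is a comparison of the text by case, followed by the routes to the endpoints.

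**1. Case by case**

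| Case | 10.5 | 10.12 | Result |
|---|---|---|---|
| Pulmonary hypertension, grade 1-2, new or worse than baseline | No hold required | Stop until resolved or baseline | Trigger differs |
| Pulmonary hypertension, grade 3 or above, treatment-related | Hold, resume one level lower | Stop, restart by risk/benefit | Hold agrees, restart differs |
| Systemic, grade 3, controlled, no crisis | Hold; one level lower if related | Treat as needed; silent on a hold | Both can be followed, but 10.12 alone would not produce a hold |
| Systemic, grade 3, uncontrolled, no crisis | Hold; one level lower if related | Reduce, with a general reference to the protocol; no hold stated | Compatible if the reference means 10.5 |
| Hypertensive crisis | Hold if grade 3 or above; one level lower if related | Stop, restart by risk/benefit | Hold agrees for grade 3 or above; restart differs |

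The missing grade for pulmonary hypertension carries meaning, because the dyspnoea item in the same section does set one (grade 3 or 4). Appendix 5 has no hypertension row, so the overlap between grade 3 and the crisis threshold in 10.12 (180 mmHg systolic or 110 mmHg diastolic) cannot be fixed from the documents.

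**2. Route to a DLT.** Criterion 1 needs grade 3 or above, so grade 1-2 pulmonary hypertension cannot meet it. Apart from the committee's discretion under criterion 5, the remaining route is criterion 4: a delay of more than 8 days within cycle 1, or of more than 14 days to cycle 2, due to significant toxicity or tolerability. The event must also be related to trial drug and attributed to the registered dose. Under 10.12 the hold can create that delay. Under 10.5 there is no hold and so no delay.

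The escalation rule in 8.1.3 turns on single patients: 0/3 escalates and 1/3 adds three patients; 1/6 escalates and more than 1/6 stops. One patient classified differently can change the decision.

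**3. Route to dose intensity.** Section 19.4 defines DI as cumulative dose divided by duration, and RDI as actual DI divided by planned DI. A full cycle at level d plans 3d over 28 days. As illustrations for a single cycle:
- A one-week delay with all doses given: (3d/35) / (3d/28) = 28/35 = 80.0%.
- One dose omitted: (2d/28) / (3d/28) = 2/3 = 66.7%.

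For the restart difference, one level down in Table 4 gives 45/56 = 80.4%, 36/45 = 80.0%, 27/36 = 75.0% or 20/27 = 74.1% of the previous dose. A risk/benefit restart fixes no dose.

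**The case against.** The case on the other side has four parts.

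- **The rules can be read together.** Section 10.5 sets a general threshold without saying that lower grades may never be held, so 10.12 could be an added event-specific rule. The ungraded Table 5 row for heart failure and other cardiopulmonary disorders might also cover pulmonary hypertension. This is a possible reading, but that row and 10.10 turn on heart-failure symptoms, ejection fraction or acute cardiac events, and nothing tells a site to place 10.12 above the routing in 9.3.3 and 10.2.
- **Systemic hypertension.** A reader might infer that 10.12 replaces the grade 3 hold with treatment, and reduces only if control fails. The text does not support that. It names no grade, does not say only, does not forbid a hold and itself stops carfilzomib in a crisis. Its reference to the protocol can be read as pointing to 10.5, Table 4 and the catch-all row. No section says to continue unchanged at grade 3. What stands is that the reference cites no section, and that 10.5 and its catch-all row differ on when a hold ends (grade 1 or grade 2, or baseline).
- **DLTs.** A reader might infer that any hypertension hold can become a DLT. A related grade 3 event held for more than 8 days under 10.5 has not returned to grade 1 or baseline, so it already meets criterion 1, and the footnote to 8.1.4 does not count the delay separately. The DLT route is therefore confined mainly to lower-grade pulmonary hypertension.
- **Size.** It is tempting to apply the 25% rate of grade 3/4 hypertension in 2.1.3.2. That rate comes from myeloma patients at 56 mg/m² without thalidomide, is not limited to cycle 1, and counts events rather than patients who would be managed differently. It does not measure this problem.

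**Conclusion.** The point holds as an internal inconsistency in the protocol. For pulmonary hypertension, 10.12 and 10.5 differ in trigger at grade 1-2 and in the restart rule at grade 3 or above when treatment-related, and precedence is not stated. For systemic hypertension the gap is smaller: 10.12 read alone may not lead to a hold for controlled grade 3 hypertension, and restart wording differs after a crisis.

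The number of patients affected cannot be estimated, because the documents give no rate of low-grade pulmonary hypertension on this regimen. For an affected patient, a one-week hold takes that cycle's relative dose intensity to about 80%, or about 67% if the dose is omitted, and in escalation cycle 1 a hold of more than 8 days could add a DLT that the other reading would not. No sample size or other stated design figure changes. The conclusion assumes that hypertension is graded by CTCAE v4.03, which the protocol uses generally, and that the hold in 10.12 refers to new or worsened pulmonary hypertension, since a patient still at baseline already meets its release condition.

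**What to change.** Reconcile protocol 9.3.3 (routing), the closing statement of 10.2, 10.5 with Table 5, 10.10 and 10.12. One way is to add one Table 5 row for pulmonary hypertension and one for systemic hypertension including crisis, each stating when carfilzomib is held, continued, reduced and restarted. The 10.12 items would then refer to those rows, and the protocol would say which section takes precedence. The general reference to the protocol in the hypertension item should name a section. The sponsor's clinicians decide the rules; this review takes no position on them.

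The cost is protocol wording, with the review and approval that any amendment needs. The SAP's endpoint definitions need no change. If patients have already been treated, listing any carfilzomib holds for either condition, with grade and cycle, would show whether sites applied the sections differently.
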